#### 10.1.1.2 CAEPR for venetoclax

Version 2.0, July 25, 2018

### Comprehensive Adverse Events and Potential Risks list (CAEPR) for Venetoclax (ABT-199, NSC 766270)

The Comprehensive Adverse Events and Potential Risks list (CAEPR) provides a single list of reported and/or potential adverse events (AE) associated with an agent using a uniform presentation of events by body system. In addition to the comprehensive list, a subset, the Specific Protocol Exceptions to Expedited Reporting (SPEER), appears in a separate column and is identified with bold and italicized text. This subset of AEs (SPEER) is a list of events that are protocol specific exceptions to expedited reporting to NCI (except as noted below). Refer to the 'CTEP, NCI Guidelines: Adverse Event Reporting Requirements'

[http://ctep.cancer.gov/protocolDevelopment/electronic\\_applications/docs/aeguidelines.pdf](http://ctep.cancer.gov/protocolDevelopment/electronic_applications/docs/aeguidelines.pdf) for further clarification. Frequency is provided based on 1298 patients. Below is the CAEPR for Venetoclax (ABT-199).

**NOTE:** Report AEs on the SPEER **ONLY IF** they exceed the grade noted in

parentheses next to the AE in the SPEER. If this CAEPR is part of a combination protocol using multiple investigational agents and has an AE listed on different SPEERs, use the lower of the grades to determine if expedited reporting is required.

Version 2.1, May 8, 2019

Adverse Events with Possible Relationship to Venetoclax (ABT-199) (CTCAE 5.0 Term) [n= 1298]		
Likely (>20%)	Less Likely (<=20%)	Rare but Serious (<3%)
BLOOD AND LYMPHATIC SYSTEM DISORDERS		
Anemia		
	Febrile neutropenia	
GASTROINTESTINAL DISORDERS		
	Constipation	
Diarrhea		
Nausea		
	Vomiting	
GENERAL DISORDERS AND ADMINISTRATION SITE CONDITIONS		
Fatigue		
	Fever	
INFECTIONS AND INFESTATIONS		
Infection 		
INVESTIGATIONS		
	Lymphocyte count decreased	
Neutrophil count decreased		
	Platelet count decreased	
	White blood cell decreased	
METABOLISM AND NUTRITION DISORDERS		
	Hypocalcemia	
	Hypokalemia	
	Hypophosphatemia	
		Tumor lysis syndrome
MUSCULOSKELETAL AND CONNECTIVE TISSUE DISORDERS		
	Arthralgia	
NERVOUS SYSTEM DISORDERS		
	Headache	
RESPIRATORY, THORACIC AND MEDIASTINAL DISORDERS		
	Cough	
VASCULAR DISORDERS		
	Hypertension	

This table will be updated as the toxicity profile of the agent is revised. Updates will be distributed to all Principal Investigators at the time of revision. The current version can be obtained by contacting [[contact]](mailto:[contact]). Your name, the name of the

investigator, the protocol and the agent should be included in the e-mail.

Infection includes all 75 sites of infection under the INFECTIONS AND INFESTATIONS SOC.

**Adverse events reported on venetoclax (ABT-199) trials, but for which there is insufficient evidence to suggest that there was a reasonable possibility that venetoclax (ABT-199) caused the adverse event:**

**BLOOD AND LYMPHATIC SYSTEM DISORDERS** - Hemolysis; Thrombotic thrombocytopenic purpura

**CARDIAC DISORDERS** - Atrial fibrillation; Cardiac disorders - Other (coronary artery disease); Heart failure; Myocardial infarction; Sinus tachycardia; Ventricular arrhythmia

**EAR AND LABYRINTH DISORDERS** - Tinnitus; Vertigo

**GASTROINTESTINAL DISORDERS** - Abdominal pain; Belching; Dry mouth; Dyspepsia; Dysphagia; Gastrointestinal disorders - Other (Crohn's disease); Small intestinal obstruction

**GENERAL DISORDERS AND ADMINISTRATION SITE CONDITIONS** - Death NOS; Edema limbs; Flu like symptoms; General disorders and administration site conditions - Other (general physical health deterioration); General disorders and administration site conditions - Other (multiple organ dysfunction syndrome); Injection site reaction; Non-cardiac chest pain; Pain; Sudden death NOS

**HEPATOBILIARY DISORDERS** - Hepatobiliary disorders - Other (hepatic function abnormal)

**IMMUNE SYSTEM DISORDERS** - Cytokine release syndrome

**INJURY, POISONING AND PROCEDURAL COMPLICATIONS** - Infusion related reaction; Injury, poisoning and procedural complications - Other (laceration)

**INVESTIGATIONS** - Aspartate aminotransferase increased; Blood bilirubin increased; Weight loss

**METABOLISM AND NUTRITION DISORDERS** - Anorexia; Dehydration; Hyperglycemia; Hyperkalemia; Hyperphosphatemia; Hyperuricemia; Hypoalbuminemia; Hypomagnesemia; Hyponatremia; Metabolism and nutrition disorders - Other (failure to thrive)

**MUSCULOSKELETAL AND CONNECTIVE TISSUE DISORDERS** - Back pain; Bone pain

**NEOPLASMS BENIGN, MALIGNANT AND UNSPECIFIED (INCL CYSTS AND POLYPS)** - Myelodysplastic syndrome; Neoplasms benign, malignant and unspecified (incl cysts and polyps) - Other (acute myeloid leukemia); Treatment related secondary malignancy

**NERVOUS SYSTEM DISORDERS** - Dizziness; Dysesthesia; Intracranial hemorrhage; Ischemia cerebrovascular; Nervous system disorders - Other (neuropathy peripheral); Peripheral sensory neuropathy; Syncope

**PSYCHIATRIC DISORDERS** - Confusion; Insomnia

**RENAL AND URINARY DISORDERS** - Acute kidney injury; Cystitis noninfective;

Dysuria

**REPRODUCTIVE SYSTEM AND BREAST DISORDERS** - Ovarian rupture

**RESPIRATORY, THORACIC AND MEDIASTINAL DISORDERS** - Allergic rhinitis; Aspiration; Dyspnea; Epistaxis; Hypoxia; Nasal congestion; Oropharyngeal pain; Pleural effusion; Respiratory failure; Respiratory, thoracic and mediastinal disorders - Other (asphyxia)

**SKIN AND SUBCUTANEOUS TISSUE DISORDERS** - Eczema; Pruritus; Rash acneiform; Rash maculo-papular

**VASCULAR DISORDERS** - Hypotension; Thromboembolic event

**Note:** Venetoclax (ABT-199) in combination with other agents could cause an exacerbation of any adverse event currently known to be caused by the other agent, or the combination may result in events never previously associated with either agent.

## 10.2 Adverse Event Characteristics

- **CTCAE term (AE description) and grade:** The descriptions and grading scales found in the revised NCI Common Terminology Criteria for Adverse Events (CTCAE) version 5.0 will be utilized for AE reporting. All appropriate treatment areas should have access to a copy of the CTCAE version 5.0. A copy of the CTCAE version 5.0 can be downloaded from the CTEP website [http://ctep.cancer.gov/protocolDevelopment/electronic\\_applications/ctc.htm](http://ctep.cancer.gov/protocolDevelopment/electronic_applications/ctc.htm).
- **For expedited reporting purposes only:**
  - AEs for the agent that are ***bold and italicized*** in the CAEPR (*i.e.*, those listed in the SPEER column, Section 10.1) should be reported through CTEP-AERS only if the grade is above the grade provided in the SPEER.
  - Other AEs for the protocol that do not require expedited reporting are outlined in Section 10.3.4.
- **Attribution** of the AE:
  - Definite – The AE is *clearly related* to the study treatment.
  - Probable – The AE is *likely related* to the study treatment.
  - Possible – The AE *may be related* to the study treatment.
  - Unlikely – The AE is *doubtfully related* to the study treatment.
  - Unrelated – The AE is *clearly NOT related* to the study treatment.

## 10.3 Expedited Adverse Event Reporting

### 10.3.1 CTEP-AERS

Expedited AE reporting for this study must use CTEP-AERS (CTEP Adverse Event Reporting System), accessed via the CTEP website (<https://eapps-ctep.nci.nih.gov/ctepaers>). The reporting procedures to be followed are presented in the “NCI Guidelines for Investigators: Adverse Event

Reporting Requirements for DCTD (CTEP and CIP) and DCP INDs and IDEs” which can be downloaded from the CTEP website

([http://ctep.cancer.gov/protocolDevelopment/electronic\\_applications/adverse\\_events.htm](http://ctep.cancer.gov/protocolDevelopment/electronic_applications/adverse_events.htm)).

These requirements are briefly outlined in the tables below (Section 10.3.3).

In the rare occurrence when Internet connectivity is lost, a 24-hour notification is to be made to CTEP by telephone at [contact]. Once Internet connectivity is restored, the 24-hour notification phoned in must be entered electronically into CTEP-AERS by the original submitter at the site.

### 10.3.2 Rave-CTEP-AERS Integration

The Cancer Therapy Evaluation Program Adverse Event Reporting System (CTEP-AERS) integration enables evaluation of post-baseline AEs entered in Rave to determine whether they require expedited reporting, and facilitates entry in CTEP-AERS for those AEs requiring expedited reporting.

All AEs that occur after baseline are collected in Medidata Rave using the Adverse Event form, which is available for entry at each treatment or reporting period, and used to collect AEs that start during the period or persist from the previous reporting period. The Clinical Research Associate (CRA) will enter AEs that occur prior to the start of treatment on a baseline form that is not included in the Rave-CTEP-AERS integration. AEs that occur prior to enrollment must begin and end on the baseline Adverse Event form and should not be included on the standard Adverse Events form that is available at treatment unless there has been an increase in grade.

Prior to sending AEs through the rules evaluation process, site staff should verify the following on the Adverse Event form in Rave:

- The reporting period (course/cycle) is correct, and
- AEs are recorded and complete (no missing fields) and the form is query-free (fields added to the form during study build do not need to be query-free for the integration call with CTEP-AERS to be a success).

The CRA reports AEs in Rave at the time the Investigator learns of the event. If the CRA modifies an AE, it must be re-submitted for rules evaluation.

Upon completion of AE entry in Medidata Rave, the CRA submits the AE for rules evaluation by completing the Expedited Reporting Evaluation form. Both NCI and protocol-specific reporting rules evaluate the AEs submitted for expedited reporting. A report is initiated in CTEP-AERS using information entered in Medidata Rave for AEs that meet reporting requirements. The CRA completes the report by accessing CTEP-AERS via a direct link on the Medidata Rave Expedited Reporting Evaluation form.

In the rare occurrence that Internet connectivity is lost, a 24-hour notification is to be made to CTEP by telephone at [contact]. Once Internet connectivity is restored, the 24-hour notification that was phoned in must be entered immediately into CTEP-AERS using the deep link from Medidata Rave.

Additional information about the CTEP-AERS integration is available on the CTSU

website:

- Study specific documents: Protocols > Documents > Education and Promotion, and
- Expedited Safety Reporting Rules Evaluation user guide: Resources > CTSU Operations Information > User Guides.

NCI requirements for SAE reporting are available on the CTEP website:

- NCI Guidelines for Investigators: Adverse Event Reporting Requirements is available at [https://ctep.cancer.gov/protocolDevelopment/electronic\\_applications/docs/aeguidelines.pdf](https://ctep.cancer.gov/protocolDevelopment/electronic_applications/docs/aeguidelines.pdf).

#### 10.3.3 Distribution of Adverse Event Reports

CTEP-AERS is programmed for automatic electronic distribution of reports to the following individuals: Principal Investigator and Adverse Event Coordinator(s) (if applicable) of the Corresponding Organization or Lead Organization, the local treating physician, and the Reporter and Submitter. CTEP-AERS provides a copy feature for other e-mail recipients.

#### 10.3.4 Expedited Reporting Guidelines

Use the NCI protocol number and the protocol-specific patient ID assigned during trial registration on all reports.

**Note: A death on study requires both routine and expedited reporting, regardless of causality. Attribution to treatment or other cause must be provided.**

Death due to progressive disease should be reported as **Grade 5 “Disease progression”** in the system organ class (SOC) “General disorders and administration site conditions.” Evidence that the death was a manifestation of underlying disease (e.g., radiological changes suggesting tumor growth or progression: clinical deterioration associated with a disease process) should be submitted.

#### **Phase 1 and Early Phase 2 Studies: Expedited Reporting Requirements for Adverse Events that Occur on Studies under an IND/IDE within 30 Days of the Last Administration of the Investigational Agent/Intervention **

##### **FDA REPORTING REQUIREMENTS FOR SERIOUS ADVERSE EVENTS (21 CFR Part 312)**

**NOTE:** Investigators **MUST** immediately report to the sponsor (NCI) **ANY** Serious Adverse Events, whether or not they are considered related to the investigational agent(s)/intervention (21 CFR 312.64)

An adverse event is considered serious if it results in **ANY** of the following outcomes:

- 1) Death
- 2) A life-threatening adverse event
- 3) An adverse event that results in inpatient hospitalization or prolongation of existing hospitalization for  $\geq 24$  hours
- 4) A persistent or significant incapacity or substantial disruption of the ability to conduct normal life functions
- 5) A congenital anomaly/birth defect
- 6) Important Medical Events (IME) that may not result in death, be life threatening, or require hospitalization

may be considered serious when, based upon medical judgment, they may jeopardize the patient or subject and may require medical or surgical intervention to prevent one of the outcomes listed in this definition. (FDA, 21 CFR 312.32; ICH E2A and ICH E6).
		

ALL SERIOUS adverse events that meet the above criteria MUST be immediately reported to the NCI via electronic submission within the timeframes detailed in the table below.
		
Hospitalization	Grade 1 and Grade 2 Timeframes	Grade 3-5 Timeframes
Resulting in Hospitalization $\geq$ 24 hrs	10 Calendar Days	24-Hour 5 Calendar Days
Not resulting in Hospitalization $\geq$ 24 hrs	Not required	

NOTE: Protocol specific exceptions to expedited reporting of serious adverse events are found in the Specific Protocol Exceptions to Expedited Reporting (SPEER) portion of the CAEPR.
		

Expedited AE reporting timelines are defined as:
 
 
○ “24-Hour; 5 Calendar Days” - The AE must initially be submitted electronically within 24 hours of learning of the AE, followed by a complete expedited report within 5 calendar days of the initial 24-hour report.
 
○ “10 Calendar Days” - A complete expedited report on the AE must be submitted electronically within 10 calendar days of learning of the AE.
 
		

Serious adverse events that occur more than 30 days after the last administration of investigational agent/intervention and have an attribution of possible, probable, or definite require reporting as follows:
 
Expedited 24-hour notification followed by complete report within 5 calendar days for:
 
 
• All Grade 3, 4, and Grade 5 AEs
 
 
Expedited 10 calendar day reports for:
 
 
• Grade 2 AEs resulting in hospitalization or prolongation of hospitalization
 
 
For studies using PET or SPECT IND agents, the AE reporting period is limited to 10 radioactive half-lives, rounded UP to the nearest whole day, after the agent/intervention was last administered. Footnote “1” above applies after this reporting period.
		

Effective Date: May 5, 2011
		

### 10.3.5 Additional Protocol-Specific Expedited Adverse Event Reporting Exclusions

For this protocol only, the AEs/grades listed below do not require expedited reporting via CTEP-AERS. However, they still must be reported through the routine reporting mechanism (Section 10.4):

CTCAE SOC	Adverse Event	Grade	$\geq$ 24h Hospitalization a
Infection	Any	Any	Regardless
Blood and lymphatic system disorders	Anemia Bone marrow hypocellular	Any	Regardless
Investigations	Lymphocyte count decreased Neutrophil count decreased Platelet count decreased	Any	Regardless

aIndicates that an adverse event required hospitalization for  $\geq$ 24 hours or prolongation of hospitalization by  $\geq$ 24 hours of a patient.

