### 6.3 Definition of Dose-Limiting Toxicity

The dose limiting toxicity period (DLT) will be defined as the time period from the start of nivolumab therapy on C1D15 to the end of cycle 3. DLT will be defined as non-hematologic toxicity of  $\geq$  grade 3 with the exception of grade 3 nausea and vomiting that resolves to  $<$  grade 3 within 72 hours, and infection (infection-related toxicities such as fever/sepsis, see below). The grade 3/4 toxicity, designated to be DLT, should be considered drug-related. Patients with transient grade  $\geq$  3 electrolyte abnormalities that are not clinically significant and are correctable within 24 hours will not be considered a DLT. Patients with  $\geq$  grade 3 transient liver function test abnormalities (AST, ALT, or alkaline phosphatase) that resolve to  $<$  grade 2 within 5 days will not be considered DLT only if it is self-limited without steroid treatment. Grade 3 or 4 infection will not constitute DLT unless it is felt that the infection resulted from unexpectedly complicated myelosuppression (degree or duration).

Hematological DLT will be considered as failure to recover neutrophil count (ANC $\geq$ 500), or platelet count  $\geq$ 25,000, or hemoglobin  $\geq$ 7 by Day 42 in patients with  $<$ 5% blasts in the bone marrow, absence of myelodysplastic changes, and/or absence of evidence of disease by flow cytometry in the bone marrow. For patients with  $\geq$  5% blasts, myelodysplastic changes, or evidence of disease by flow cytometry/cytogenetics, failure to recover neutrophil, platelet count, or hemoglobin may not be considered DLT as this could be the result of persistent disease.

Specifically with nivolumab, any patient who requires high dose steroids (any dose greater than the equivalent to 20 mg prednisone daily) will be considered to have experienced a DLT and will be taken off nivolumab but allowed to remain on decitabine and venetoclax.

Management and dose modifications associated with the above adverse events are outlined in Section 7.

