### 13.2.2 Responsibility for Data Submission

For ETCTN trials, it is the responsibility of the PI(s) at the site to ensure that all investigators at the ETCTN Sites understand the procedures for data submission for each ETCTN protocol and that protocol specified data are submitted accurately and in a timely manner to the CTMS via the electronic data capture system, Medidata Rave.

Data are to be submitted via Medidata Rave to CTMS on a real-time basis, but no less than once every 2 weeks. The timeliness of data submissions and timeliness in resolving data queries will be tracked by CTMS. Metrics for timeliness will be followed and assessed on a quarterly basis. For the purpose of Institutional Performance Monitoring, data will be considered delinquent if it is greater than 4 weeks past due.

Data from Medidata Rave and CTEP-AERS is reviewed by the CTMS on an ongoing basis as data is received. Queries will be issued by CTMS directly within Rave. The queries will appear on the Task Summary Tab within Rave for the CRA at the ETCTN to resolve. Monthly web-based reports are posted for review by the Drug Monitors in the IDB, CTEP. Onsite audits will be conducted by the CTMS to ensure compliance with regulatory requirements, GCP, and NCI policies and procedures with the overarching goal of ensuring the integrity of data generated from NCI-sponsored clinical trials, as described in the ETCTN Program Guidelines, which may be found on the CTEP

([http://ctep.cancer.gov/protocolDevelopment/electronic\\_applications/adverse\\_events.htm](http://ctep.cancer.gov/protocolDevelopment/electronic_applications/adverse_events.htm)) and CTSU websites.

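### Section 10.3.5 exempts infection and five listed marrow or count terms from expedited reporting at any grade, with no exception for Grade 5, and so conflicts with the rule in Section 10.3.4 that every death is expedited

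*Combined protocol and SAP*

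**What the plan says.** Section 10.3.4 sets the general rule for deaths: "A death on study requires both routine and expedited reporting, regardless of causality". The table that follows in the same section counts death first among the outcomes that make an event serious. On such events it says: "adverse events that meet the above criteria MUST be immediately reported to the NCI via electronic submission within the timeframes detailed in the table below". For Grades 3-5 that timeframe is a 24-hour notice and a complete report within 5 calendar days. The only source of exceptions it names is the SPEER column of the CAEPR.

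Section 10.3.5 then adds exclusions: "For this protocol only, the AEs/grades listed below do not require expedited reporting via CTEP-AERS". The infection row reads "Infection Any Any Regardless", the columns being class, event, grade and hospitalization of 24 hours or more. A second row covers anemia and bone marrow hypocellular. The third covers lymphocyte count decreased and ends "Neutrophil count decreased Platelet count decreased Any Regardless". The text keeps one route open for these events: "However, they still must be reported through the routine reporting mechanism (Section 10.4".

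The routine route is described in Section 13.2.2: "Data are to be submitted via Medidata Rave to CTMS on a real-time basis, but no less than once every 2 weeks".

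**The concern.** The protocol uses Grade 5 for death: Section 10.3.4 has deaths from progressive disease reported as Grade 5, and its timeframe column runs from Grade 3 to Grade 5. An exclusion at any grade therefore takes in a fatal infection on its plain words. The coordinator at a site where a patient dies of sepsis reads one section that requires the expedited report and the next section that waives it.

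At stake is the 24-hour notice of a death to the sponsor. The primary objective is safety and the MTD of a new triplet, cohorts are small, and enrolment decisions follow the toxicity seen so far. Notice of a death should not depend on which of two adjacent sections a site happens to apply.

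**Working it through.** The plan gives no figure for this point, so the check is mainly a comparison of texts.

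**1. Does the exclusion reach deaths?** The grade column says *Any* in all three rows. No footnote or sentence in 10.3.5 excepts Grade 5; the only footnote defines the hospitalization column. So it does on its wording.

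**2. Does any text settle which section prevails?**
- 10.3.4: the death rule is unconditional and does not mention 10.3.5. Its note on exceptions points only to the SPEER.
- 10.3.5: described as specific to this protocol, but it does not say that it overrides 10.3.4.
- 10.3.2: NCI rules and protocol-specific rules are both applied when an AE is submitted in Rave. Neither set is given priority.
- 10.2: sends the reader to 10.3.4 for the other events that need no expedited report, although that list is in 10.3.5. Section 10.3.1 has the same kind of slip: it places the reporting tables in 10.3.3, and they are in 10.3.4.

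Nothing resolves the conflict.

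**3. Does the SPEER agree with 10.3.5?** The nivolumab SPEER in 10.1.1 compares with 10.3.5 as follows:

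| Term | Nivolumab SPEER | 10.3.5 |
|---|---|---|
| Anemia | exempt up to Grade 3 | any grade |
| Lymphocyte count decreased | exempt up to Grade 4 | any grade |
| Neutrophil or platelet count decreased | no entry | any grade |
| Infection, bone marrow hypocellular | no entry | any grade |

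Grade 4 anemia is thus expedited under the SPEER and exempt under 10.3.5. Limiting the rows to Grades 1-4 would make the lymphocyte entry match the SPEER exactly. The anemia entry would still differ at Grade 4.

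**4. What changes for a site that follows 10.3.5?** Inputs: 24 hours (10.3.4), at most 2 weeks between submissions (13.2.2), and 2-3 patients per month (9.2). Patients enrolled while a report is pending = monthly rate x days / 30.4.
- 1 day: 2 x 1 / 30.4 = 0.07 to 3 x 1 / 30.4 = 0.10
- 14 days: 2 x 14 / 30.4 = 0.92 to 3 x 14 / 30.4 = 1.38

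The 14-day line is the outer limit for a compliant site, not the expected delay.

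**5. How often might the question arise?** Section 2.4.1 cites a 30-day mortality of 3.6% for 10-day decitabine with venetoclax. If that rate applied to the maximum of 42 patients, expected early deaths = 42 x 0.036 = 1.5, and the chance of at least one = 1 - 0.964^42 = 0.79. The documents do not give the share due to infection. Assuming 25% gives 0.4 such deaths, and assuming 100% gives 1.5. These are occasions on which the two sections would collide, not reports that would be lost.

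**The case against.** The strongest reply is that the two sections can be read together: 10.3.5 exempts listed AE terms, while death is a separate trigger that 10.3.4 keeps whatever the term. The NCI rules stay active in the Rave integration. This stands to the extent that nobody can say 10.3.5 wins. A reader might infer that it does, because it is the later and more specific text, and conclude that fatal infections reach the sponsor only through routine entry. The documents state no such precedence. Equally, they do not state the harmonizing reading, and a site should not have to supply it.

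The second reply concerns delay. Section 10.3.2 has AEs entered in Rave when the investigator learns of them, 13.2.2 asks for real-time submission, and 13.1 gives the principal investigator and statistician access to the data at all times. This also stands, and it is why the 14-day figure is only an outer limit. A reader might add the 4-week delinquency margin in 13.2.2 and speak of 42 days. That margin is a performance metric for late data, not a permitted reporting interval. Even so, none of these provisions is a timed alert to the sponsor.

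The third reply concerns dose-limiting toxicity. Section 6.3 says "Grade 3 or 4 infection will not constitute DLT unless it is felt that the infection resulted from unexpectedly complicated myelosuppression (degree or duration", and it also makes failed count recovery by Day 42 a DLT. A reader might infer that exempting these events contradicts the dose-finding rules. It does not. For non-fatal events 10.3.5 is a labelled, deliberate exclusion, and nothing in the documents makes CTEP-AERS the route by which DLTs are notified. A rule for timed DLT notice could be worth having, but it is a separate and optional suggestion.

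Finally, the exclusion covers five named marrow and count terms, not all cytopenia. Febrile neutropenia and white blood cell decreased are not in the table.

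**Conclusion.** The point holds as a conflict between 10.3.4 and 10.3.5 for Grade 5 events in the listed terms. In practice, fatal infection is the case to settle. There is a lesser mismatch with the SPEER for Grade 4 anemia; it is less sharp because 10.3.5 is headed as additional to the other exceptions and can be read as widening them.

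For a site that follows 10.3.5, the consequence is a notice at the pace of routine entry instead of within 24 hours. In the worst compliant case, about one further patient (0.9-1.4) enrols in the interval. That rests on the stated accrual rate and on the full 14 days being used.

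The figure of 1.5 early deaths rests on carrying over a rate from a study of several AML groups. Part of its 30-day window falls before nivolumab starts on Day 15, and it leaves out deaths on study after 30 days. The infectious share is an assumption, so that figure gives scale only; the conclusion does not depend on it. No analysis, dose rule or error rate in the plan is affected. The correction is nevertheless needed, because notification of deaths should have one reading.

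**What to change.** - In the 10.3.5 table, change the grade from *Any* to *Grades 1-4* in all three rows.
- Add one sentence: Grade 5 events, including fatal infections, are always reported under Section 10.3.4.
- Reconcile the anemia row with the Grade 3 limit in the nivolumab SPEER, and say which governs Grade 4 anemia.
- In 10.3.4, name 10.3.5 beside the SPEER as a source of exceptions for non-fatal events.
- Correct the cross-reference in 10.2 to 10.3.5 and, at the same time, the one in 10.3.1 to 10.3.4.
- Check that the protocol-specific rules in the Rave/CTEP-AERS integration match.

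The cost is a table edit, a few sentences and a rules update, plus a few more expedited reports. Non-fatal infections and the listed count decreases stay exempt, apart from whatever is decided for Grade 4 anemia. If the sponsor also wants timed notice of DLTs, that is better written as its own rule than attached to this exclusion table.
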